Physical Measures. The integrity of physiological measure will be maintained by having multiple research staff trained by local UCSD experts in the use of the inclinometer, dynamometer, heart monitors, and core strength tests. Following initial training, research staff will conduct a series of 6 mock measurements to ensure reliability of measurement. Any problems will be tracked and addressed with re-training.

Spinal Range of Motion (ROM) will be measured using a digital inclinometer, which isolates lumbar

ROM (flexion and extension). The device uses a precise optical angular scanner placed along the spine. Device error is negligible with accuracy as high as 98%¹²¹ The device has been used in other yoga interventions.¹⁰³

Grip Strength will be measured using two trials for each hand with a hydraulic dynamometer. The best performance is selected for each side, and the average of the left and right hand is used for analysis. Painful or injured hands or wrists are not tested and the result of the good hand is used. Reliability has been shown to be high: $r=0.88-0.92$. Good predictive validity of grip strength has been shown for disability and mortality.¹²²

Core Stabilization and Strength. Prone and supine bridge positions will assess core stabilization.¹²³ Participants begin on their elbows in the prone position with shoulders, hips, and ankles aligned. The supine position is tested next, with knees flexed 90 degrees and pelvis raised from the floor with shoulders, hips, and knees aligned. Assessors record length of time (120 seconds max) that each position is held in proper form.

Heart rate. Physical exertion during yoga will be measured using Polar FT4 Heart Rate Monitors. Worn on the chest, they provide aggregate summary data such as maximum and mean heart rate during a workout.

Interventions:

There will be two interventions: Hatha Yoga and Restorative Yoga. Both interventions will meet 2 times a week for 12 weeks with at least one day of rest between each class. Individual classes will be 60 minutes long and led by a certified yoga instructor. Additionally, participants will be encouraged to practice yoga at home as guided in a home practice manual.

Hatha Yoga (HY)

Using information gathered during qualitative interviews in Phase I, the yoga intervention will be tailored to our target population. However, we do not anticipate significant changes to the existing yoga protocol for CLBP that was developed for [name] current study, Yoga for CLBP being conducted with veterans. Our team of experienced yoga instructors will also adapt the existing CLBP yoga intervention to be safe and effective for CNP. Our team consists of co-investigator [name] (researcher and experienced yoga instructor), [name] (current instructor of Yoga for CLBP at VASD), [name] (owner of Yoga Oceanside), and [name] (military yoga instructor at NMCSW Wellness Program). We will also consult *Anatomy of Hatha Yoga*⁷⁹ and *Yoga as Medicine* which has a useful section on avoiding neck injuries.⁹³ Poses known to put pressure on joints, muscles, or nerves in the neck such as head stands, shoulder stands including plow and other variations will not be used.

The HY intervention will be led by a certified instructor at each site. Both instructors will be trained by [name] who has been practicing yoga for over 16 years and has over 8 years of teaching experience and is the main instructor for [name] for Vets with CLBP. (NOTE: We will model the HY intervention after the current Yoga for CLBP intervention which is a classical hatha yoga with influences from Viniyoga and Iyengar yoga. Both Viniyoga and Iyengar yoga styles emphasize modifications and adaptations including the use of props such as straps and blocks in order to minimize the risk of injury and make the poses accessible to people with health problems and limitations.) The certified yoga instructors will lead participants through a series of 23 yoga poses (32 total variations) at a slow-moderate pace. Instructors will be asked to follow the manual which will help standardize the yoga intervention. The manual contains pictures and a description of how to perform each pose with typical instructor dialogue. The dialogue may be paraphrased and varied slightly, yet promotes more consistent replication and generalization of results. The manual includes some poses that could aggravate back conditions if they are not modified for some people. That is why multiple modifications are shown and many of the poses shown are only worked up to after weeks of practice and individual attention from the instructor. The more challenging poses are not included in the home practice manuals. The importance of attending all sessions will be stressed during session 1 and throughout all sessions. Participants who miss a session without notifying the instructor will be contacted to check on the reason for non-attendance. Participants will also receive a home practice manual containing some basic, safe postures that can be performed in 10-15 minutes on days they will not be attending the formal in-person sessions. Participants will be encouraged to not push themselves as much when practicing at home and to stop when pain or discomfort becomes noticeable. They will be encouraged to consult with the instructor individually before and after

class about any problems or difficulties they are encountering at home or in the formal sessions.

During the formal sessions, participants will be instructed to take slow, deep breaths in conjunction with specific phases of poses. Participants will be encouraged to emulate the optimal alignment being demonstrated by the instructor. In addition, participants will be encouraged to focus on a goal or positive direction for their yoga practice. The yoga classes are constructed to allow optimal flow from one pose to another. Each 60-minute session will begin with a few minutes of deep breathing and mindfulness/meditation followed by about 15 minutes of basic postures (Poses 1-8) to warm-up the muscles/body by increasing circulation, providing more flexibility as the class progresses. Most poses will be conducted once to each side or with the opposite foot leading. After warming-up, the instructor will lead students through a series of standing poses (Poses 9-14) which include balance for about 15 minutes. After the standing poses, the class will move into floor poses (Poses 15-22) for about 20 minutes. Each session will end with about 5-7 minutes of complete relaxation in the standard ending pose “savasana”. At this time, additional positive mental suggestions/affirmations will be provided.

Restorative Yoga (RY)

RY will serve as the comparison intervention but is also of interest in itself as a possible treatment modality. For the purposes of this pilot study (R34 proposal), we are using the term “Restorative Yoga” to refer to yoga interventions that emphasize relaxation and include very little movement, and are non-strenuous. RY sessions typically include only 5-10 poses, mostly done lying down, eyes are often closed, with bolsters and/or blankets used for comfort and warmth. Because eyes are often closed, and movement is limited, the instructor typically provides more instructions on deep breathing techniques and guided imagery.

The details of the RY intervention will be developed using the expertise of our team of experienced yoga instructors and the feedback from the Phase 1 Qualitative Interviews. Our yoga experts have training and experience delivering RY sessions. The team will read and discuss *The iRest Program for Healing PTSD*,¹⁰¹ a recent book that outlines the iRest approach to treating PTSD. The team will also review and discuss a RY practice manual developed for metabolic syndrome by our colleagues at UCSD and UCSF. The 42-page manual explains 5 different poses with an additional 8 modifications to those poses, and provides pictures and helpful tips. Based on these materials, our yoga experts will develop our RY intervention and create an intervention manual and a home practice manual. The intervention will occur 2x weekly for 12 weeks – each class will be 60 minutes to match that timeframe of the active yoga intervention.

Treatment Fidelity.

Instructor fidelity to the yoga intervention manual will be evaluated using video recordings of yoga intervention sessions. All yoga sessions will be recorded with a digital camcorder and tripod placed in the back of the yoga room. Instructors and participants will be aware of and consent to the recordings. We do not plan to analyze all recorded sessions, but recording all sessions will standardize the presence of the camera across all sessions and result in more rapid habituation. Of the 24 sessions videotaped at each site, we will randomly select a session from weeks 1-4, weeks 5-8, and weeks 9-12 for review by a yoga instructor from Yoga Oceanside. They will review the sessions using a manual checklist for instructor adherence to the yoga manuals, which will consist of a Yes/No, blank, and 0-10 rating scale for each procedure or instruction.

Data management. Questionnaires will be formatted by the project coordinator under the supervision of [name] (PI). Formatting will be designed to reduce recording errors and facilitate computer scanning and verification. Forms will be de-identified to protect confidentiality, and data will be scanned and verified by the data manager (and project coordinator). The project coordinator will monitor the quality of the questionnaire data as soon as they are collected to achieve prompt resolution of errors and omissions. Data will be stored on a password protected secure network server at UCSD. Access privileges are limited to essential staff.

Statistical Management and Analysis: Qualitative data will be managed and analyzed by Co-I [name]. Results will be presented to the research team and additional sub-analyses will be conducted as needed before the intervention is modified. Health outcome data and mediational variables will be collected directly before and after the 12-week yoga program using physiological assessments and questionnaires. We will assess the effect size of the difference in change in health outcomes (pain interference, pain severity, and physical functioning) from pre- to post-intervention between

intervention groups using a linear random effects model. We will assess clustering by site with a likelihood ratio test. The point estimate of difference in change score between two groups and the 95% confidence interval for the estimated difference will be provided. We will also perform multivariate analysis and an adjusted effects size (with 95% CI) by including baseline characteristics that are significantly imbalanced between two groups as covariates in the random effects model. Analyses will be conducted by the biostatistician ([name]). The effect size estimates (and CI width) will help inform power calculations for the subsequent R01 submission. R software packages will be used for all statistical analyses.

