Aim 2: Evaluate the acceptability of and preferences for yoga interventions among active-duty military personnel with CLBP/CNP. 30 total Qualitative Interviews will be conducted with military personnel with CLBP or CNP and with healthcare providers who provide yoga or other healthcare to military personnel with CLBP or CNP.

Qualitative Interview Methods:

The proposed qualitative component of the study is both exploratory and inductive in nature. Semi-structured qualitative interviews will be employed to explore the participant preferences and experiences with yoga in relation to their CLBP/CNP. This information will contribute to the refinement of an existing yoga intervention for veterans with CLBP so that it is optimal for active-duty military personnel. Interview techniques will use open-ended questions to stimulate a wider range of responses for a more complete understanding of the needs and attitudes encountered by study participants. Interviews are expected to last about 60 minutes in length. Open-ended questions during the interviews will address: 1) past experiences with non-pharmacological treatments for CLBP/CNP; 2) past experiences with yoga; 3) a brief presentation of the existing yoga program; 4) preferences in regard to the emphasis given to the various components the yoga intervention such as postures, pace of transition through poses, breathing techniques, meditation, ethical principles and spiritual aspects; 5) dosing of yoga; and 6) discussion of research participation and burden given military schedules. Interviews with yoga providers and other health care providers will follow the same set of questions but will ask for both their own preferences as a clinician and their perspective on how their patients

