Aim 3: Modify an existing yoga intervention for the preferences of active-duty military and to address both CLBP and CNP. Based on the results of the qualitative interviews, the existing yoga intervention designed for VA patients with CLBP will be refined and adjusted to better fit the preferences of active-duty military personnel with CLBP or CNP. This process will start with the investigators and yoga experts reviewing [name] report of the qualitative results. The team will also independently review a current Yoga for CLBP manual being used by [name], the Cramer et al. manuscript which lists the 14 yoga poses they selected for treating CNP, and other yoga texts. Investigators and experts will then convene at UCSD for an extended afternoon meeting to select of a pool of possible poses. The PI will then work with orthopedic surgeon [name] and yoga expert [name] to propose specific changes to the intervention. The revisions will be presented to the other collaborators for review and additional discussion. Possible examples include a slightly faster pace, adding postures for additional challenge for those with less impairment (yet easily modified to be safe for all), additional attention tasks or imagery, and further trauma sensitivity. All changes and the rationale behind them will be documented.

Phase 2

Please note: before we begin Phase 2 we will also need to obtain IRB approval from NMCS D for activities that will take place at that site. Once we obtain IRB approval from NMCS D, we will provide a copy to UCSD's IRB prior to commencing any activities at that site. In Phase 2 we will accomplish Aims 4-6 by conducting a pilot RCT with 2 yoga interventions. We will recruit 25 people at each of two sites, one in a military medical facility (NMCS D) and one in a community yoga studio (Yoga Oceanside) near a large military base for a total of 50 participants. Once 25 people have been recruited at each site, they will be randomized to attend either active hatha yoga or restorative yoga.

Screening and Inclusion/Exclusion Criteria.

50 active-duty military personnel with CLBP will be recruited and randomized to either active hatha yoga or to restorative yoga. Inclusion criteria are as follows:

Inclusion:

- Diagnosis of CLBP or CNP > 6 months
- Willing to attend a yoga program for 12 weeks
- Willing to complete 3 assessments
- English literacy
- Have had no changes in pain treatments in the past month

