- Willing to not change pain treatments during study unless medically necessary
- Have not practiced yoga more than 2x in the last 12 months

Exclusion:

- Back or neck surgery within the last year
- Back or neck pain due to specific systemic problem (e.g., lupus, scoliosis)
- Severe vertebral disk problems,
- Persistent sciatica or nerve compression > 3 months
- Coexisting chronic pain problem (e.g., migraine headaches, fibromyalgia)
- Serious or unstable psychiatric illness (e.g., psychosis, mania, episode, or substance dependence)
- Major coexisting medical illness (e.g., cancer, COPD, morbid obesity)
- Positive Romberg test (with or without sensory neuropathy)

No other exclusion criteria will be employed. No special classes of subjects or other vulnerable populations will be recruited. We will make efforts to recruit at least representative proportions of women and racial and ethnic minorities. More detail is provided on the inclusion of women and minorities document in this application.

Inclusion Criteria	Determined by:	Exclusion Criteria	Determined by:
Active-duty military employment and age ≥ 18	screening interview; medical record	back or neck surgery within the last 1 year	screening interview; medical record
Diagnosis of chronic low back or neck pain > 6 months	screening interview; medical record	back or neck pain due to specific systemic problem (e.g., lupus)	screening interview; medical record
Willing to attend 12-weeks of yoga	screening interview; informed consent	severe vertebral disk problems	screening interview; medical record
Willing to complete 2 assessments	screening interview; informed consent	persistent sciatica or nerve compression > 3 months	screening interview; medical record
English Literacy	screening interview; informed consent	coexisting chronic pain problem (migraine headaches, fibromyalgia)	screening interview; medical record
No changes in pain treatments in the past month.	medical record; screening interview	Serious or unstable psychiatric illness (e.g. psychosis, mania)	screening interview; medical record
Willing to not change pain treatments during study unless medically necessary.	screening interview; informed consent	major coexisting medical illness (e.g., cancer, COPD, morbid obesity)	screening interview; medical record
Have not practiced yoga > 2x in the last 12 months	screening interview; informed consent	Positive Romberg test (with or without sensory neuropathy)	screening interview; medical record

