20. COMPENSATION FOR PARTICIPATION

Phase 1: Qualitative Interviews – 30 participants will receive a \$30 gift card to Trader Joes for participating in a 60 minute interview.

Phase 2: Yoga Interventions – 50 participants will receive 24 free 1-hour yoga classes (12 weeks of 2 classes per week), plus a \$30 gift card to Trader Joes for each assessment attended (\$30 x 2 assessments = total of \$60 in gift cards).

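### The primary outcome has one post-baseline value, at week 12, and no remote route to it is described, so active-duty participants away on duty would have no change score

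*Combined protocol and SAP*

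**What the plan says.** **Who is enrolled.** Phase 2 takes only serving personnel; the criteria table in Section 9 reads "Active-duty military employment and age ≥ 18". The criteria closest to availability are "Willing to attend a yoga program for 12 weeks" (in the table, "Willing to attend 12-weeks of yoga") and "Willing to complete 3 assessments" (in the table, "Willing to complete 2 assessments"). The table has both settled by screening interview and informed consent. Neither the lists in Sections 9 and 10 nor the table mentions orders, deployment, transfer, separation or planned absence. The exclusion list closes with "No other exclusion criteria will be employed".

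**When and how the outcome is collected.** Section 9 (Assessments and Randomization) schedules assessments before the intervention and at 12 weeks. Each starts with 20 to 30 minutes of questionnaires, the BPI among them, followed by about 10 minutes of physical measures by a research assistant. Data management describes forms designed for scanning. Section 9 pays $30 for completing each assessment; Section 20 pays it "for each assessment attended". The self-reports at weeks 4 and 8 cover treatments and treatment changes only.

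**How it is analysed.** Statistical Management and Analysis fits a linear random effects model to pre-to-post change. It reports the difference with a 95% CI and passes the effect size and CI width to the R01 power calculation. It names no missing-data method and no dropout allowance.

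**Military schedules.** These appear as a Phase 1 interview topic: "discussion of research participation and burden given military schedules".

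**The concern.** People on active duty do not fully control where they will be in three months. A candidate can be sincerely willing to attend and already have orders to be elsewhere. That candidate meets every written criterion, and nothing requires staff to ask. If the person is away at week 12, the only post-baseline value of the primary outcome is lost, although the BPI is a questionnaire and needs no hands-on measurement. The random effects model can keep the baseline row, but that row adds almost nothing to an estimate of change.

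Two products of the pilot are affected. One is the precision of the effect size estimate (Aim 6), since CI width is itself an input to the next trial. The other is the meaning of the retention and attendance figures (Aim 5): duty absence and loss of interest call for different responses in a full trial, and the plan has no field that separates them throughout.

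**Working it through.** **No figure to reproduce.** The documents give no power, SD, effect size or dropout rate, and Section 17 says the study is not powered for efficacy. The only sample size arithmetic is 2 sites × 25 = 50. The size of the problem has to be shown over assumed losses.

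**Step 1: is there another route to a week 12 value?** Reading Section 9 (Assessments and Randomization, Data management) beside Section 20 gives one assessment, questionnaires first, staff measures next, scannable forms, and payment worded once by completion and once by attendance. There is no visit window, early-departure assessment or remote option. The week 4 and 8 contacts do not collect the BPI. Absence at week 12 therefore means no change score, unless staff improvise.

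**Step 2: can availability change after screening?** The opening of Phase 2 randomises once 25 people have been recruited at a site. Assessments and Randomization places randomisation after the baseline assessment. If randomisation is held until a site reaches 25, early recruits may wait, and no recheck is described.

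**Step 3: precision.** Let N be the number randomised, m the share missing at week 12, and n = N(1 − m)/2 per arm. In SD units of the change score,

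half-width = t(0.975, 2n − 2) × √(2/n).

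This assumes 1:1 allocation, no clustering by site and equal loss in both arms. For N = 50:

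| Missing, any cause (assumed) | With week 12 data | n per arm | Half-width (SD) | Ratio to no loss |
|---|---|---|---|---|
| 0% | 50 | 25 | 0.569 | 1 |
| 10% | 45 | 22.5 | 0.601 | 1.056 |
| 20% | 40 | 20 | 0.640 | 1.125 |
| 30% | 35 | 17.5 | 0.688 | 1.209 |

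The synopsis in Section 5 says 60 rather than 50. With N = 60 the half-widths are 0.52, 0.55, 0.58 and 0.62 SD, the same pattern.

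**Step 4: enrolment equivalent.** To keep 50 participants with week 12 data, N = 50/(1 − m): 50/0.9 = 55.6, so 56; 50/0.8 = 62.5, so 63; 50/0.7 = 71.4, so 72.

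**Step 5: what remote collection could return.** As an illustration only: if 20% (10 of 50) would miss the visit and half of them completed the questionnaires remotely, 45 would have a BPI value. The half-width would be 0.601 rather than 0.640 SD. Physical measures would still be missing for all 10.

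**The case against.** **Attended-only collection is inferred.** It rests on the sequence of the assessment, the scannable forms and one phrase in the compensation section; Section 9 speaks of completing an assessment. No passage forbids a telephone or mailed questionnaire. This stands: the defect is that no route is specified, not that one is ruled out.

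**The willingness criteria already do some work.** The sentence quoted above closes the exclusion list only. A candidate must also affirm willingness for 12 weeks, and a screener could turn away someone who discloses orders. That is true, but disclosure is left to chance and the answer is not recorded.

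**Reasons for absence are partly collected.** The Hatha Yoga section has staff contact participants who miss a session without notice. The acceptability questions ask about influences on attendance. Phase 1 interviews cover schedules, and Section 11 says they will shape recruitment. These provisions count. They leave out absences notified in advance, the contact rule is written only for hatha yoga, and none supplies a duty or personal code or a reason for a missed week 12 assessment.

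**Absence is feasibility data.** Aims 4 and 5 measure recruitment and adherence in this population. A reader might infer that people with known orders should be excluded. The documents do not support that step: exclusion would raise observed retention, lower recruitment yield and hide part of what the pilot is meant to learn. This objection stands in full.

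**The losses are assumed and not specific.** They cover dropout from any cause, and the same widening would apply to any trial of 50. This also stands, and it limits what the table can show.

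**Conclusion.** The gap is real, of moderate size and cheap to close. The plan describes no way to obtain the single post-baseline value of a self-report primary outcome from a participant who cannot attend, in a population whose presence is partly decided by others. At assumed losses of 10%, 20% and 30% from any cause, the 95% CI half-width grows from about 0.57 SD to 0.60, 0.64 and 0.69 SD. Remote collection would recover an unknown part of that, because some of the loss will be people who have stopped responding.

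Two stronger conclusions might be drawn and should not be.

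- **That these losses are predictable at screening.** The documents give no rate of absence and no share of it that would be known in advance.
- **That loss will differ by arm because of class times.** No timetable is given, and both arms meet twice a week for 60 minutes over 12 weeks. With equal missingness and the same gap between leavers and stayers in both arms, the bias from this source is zero.

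Since the study disclaims efficacy conclusions, the consequence is a less informative input to the next trial, not a wrong efficacy claim.

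**What to change.** 1. **Section 9, Assessments and Randomization:** allow the BPI and the other questionnaires at week 12 by telephone, mail or secure web for anyone who cannot attend, and record the mode used. Only the physical measures are then missing.
2. **Section 20:** tie the $30 to completing the assessment, as Section 9 does. Section 19 notes that some serving personnel may be unable to accept payment, so this removes an obstacle for some, not all.
3. **Screening, and again before randomisation:** ask about known orders or planned absences over the 12 weeks and record the answer. Do not make it an exclusion.
4. **Both arms:** code each missed class and each missed week 12 assessment as duty or personal, and report retention and attendance both ways.
5. **While editing:** reconcile the number of assessments in the criteria (3 in the lists, 2 in the table).

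The cost is short protocol wording, a remote form and two recorded fields. The statistical downside is a mixed mode of questionnaire collection for a few participants. Recording the mode lets the analysis show how many were affected.

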All eligible participants will be scheduled for assessments at two time points: pre (baseline) and post intervention (12-weeks). The assessments consist of a battery of 8-10 questionnaires taking about 20-30 minutes to complete. Next, physiological measurements will be conducted by a trained research assistant and will take about 10 minutes to complete. Participants will receive \$30 for completing each assessments. Completed questionnaires will be coded with a study ID to protect confidentiality. All personal health information will be entered into a password protected secure server environment within UCSD-HSRC. After the baseline assessment, participants will be randomized to either the Hatha Yoga Intervention or to the Restorative Yoga Intervention. Randomization will occur through a web portal linked to a secure file providing block randomized digits that was prepared by the study statistician. There will be one block file for each site, with 30 digits in each file, allowing each site to have a balanced randomization. Research staff will not have access to the randomization file. Participants will be told of their group assignment and will be allowed to ask additional questions at that time.

Assessment Questionnaires and Measurements:

Screening: Medical record information will be used by screening physicians to complete the Back Pain History Questionnaire which will allow the investigators to assign a descriptive diagnosis based on the Quebec Nomenclature on Activity Related Spinal Disorders¹⁰⁴. The measure has been used in previous VA studies¹⁰⁵⁻¹⁰⁷. Additional information on co-morbid diagnoses, opioid pain medication usage, and ongoing treatments will also be collected including information on TBI, PTSD and other psychological diagnoses, and substance use.

Demographics: A brief questionnaire will assess age, gender, education, race/ethnicity, employment status, military rank and duties, and combat status.

Pain interference with daily function and pain severity will be measured with the short version of the Brief Pain Inventory (BPI).¹⁰⁸ Pain interference will serve as the primary outcome. The BPI has been validated with CLBP.¹⁰⁹ The pain interference score is the mean of the 7 interference items. The pain severity score is the mean of 4 severity items. The BPI has good reliability (alpha 0.77 - 0.91).

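### The plan has no provision to keep the week 12 assessor of the physical measures unaware of arm; the judged bridge times are the most exposed

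*Combined protocol and SAP*

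**What the plan says.** All of this is in Section 9.

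- **Who measures.** Under Assessments and Randomization, "physiological measurements will be conducted by a trained research assistant and will take about 10 minutes to complete". Physical Measures adds that measurement quality rests on "having multiple research staff trained by local UCSD experts in the use of the inclinometer, dynamometer, heart monitors, and core strength tests", followed by 6 mock measurements and re-training where problems appear.
- **When.** There are two assessments, baseline and 12 weeks. Allocation comes between them: "After the baseline assessment, participants will be randomized to either the Hatha Yoga Intervention or to the Restorative Yoga Intervention".
- **What is concealed.** "Research staff will not have access to the randomization file".
- **What is disclosed.** "Participants will be told of their group assignment and will be allowed to ask additional questions at that time".
- **What is judged.** For the two bridge positions, "Assessors record length of time (120 seconds max) that each position is held in proper form". The text describes the body alignment for each position but gives no tolerance, warning or stopping rule for loss of form.
- **What depends on effort.** "Grip Strength will be measured using two trials for each hand with a hydraulic dynamometer". No script for encouragement is given. Spinal range of motion is read from a digital inclinometer.

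The available text does not say that the assessor is masked or separate from staff who have other contact with the participant. Nor does it ask participants to withhold their class type.

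**The concern.** Blocking access to the randomisation file protects the sequence until a participant is assigned. It has no bearing on what the person holding the stopwatch knows 12 weeks later. By then the participant knows the arm and has attended up to 24 classes, and may mention them in passing.

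Other routes are possible. Section 12 has a research assistant take consent. Section 9 has staff ask about treatment changes at 4, 8 and 12 weeks, and a weekly home log records pose difficulty and exertion. The plan does not say that one person does several of these tasks for the same participant, but it does not prevent it.

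An assessor who knows the arm could call loss of form earlier or later, or encourage one group more. What is at stake is the between-arm difference in bridge time and, to a lesser degree, grip strength, together with any mechanism work that uses them. Section 9 says that mechanisms will be studied and that mediational variables are collected.

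**Working it through.** The plan has no power calculation and no figure for these measures, so there is nothing to reproduce. The check is mainly textual, with a small illustration.

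**1. Where a bias can enter.** The baseline measurement precedes randomisation, so knowledge of arm cannot affect it. Only week 12 is exposed. Leniency that is equal in both arms cancels from the between-arm difference. Leniency that differs by arm passes in full into the difference in change.

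**2. Exposure by measure (Physical Measures).**

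| Measure | What the assessor controls | Exposure |
|---|---|---|
| Prone and supine bridge, capped at 120 s | Decides when form is lost; encouragement | Greatest |
| Grip, two trials per hand, best kept | Encouragement; the instrument gives the reading | Smaller |
| Spinal range of motion, digital inclinometer | Placement and prompting; the reading is digital | Least |
| Heart rate monitor | Worn during classes; not rated by an assessor at week 12 | None here |

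**3. Which outcomes are outside the problem.** The primary outcome, BPI pain interference, is a questionnaire score. Statistical Management and Analysis names pain interference, pain severity and physical functioning for the effect-size model. Section 9 measures disability and physical function with the Roland-Morris and Neck Disability questionnaires. Grip and bridge times are not named for that model.

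**4. Illustration of size (assumed inputs).** Section 9 plans 50 participants, so about 25 per arm. The standard error of a standardised difference is sqrt(2/25) = 0.283, and the 95% half-width is 1.96 × 0.283 = 0.554 SD.

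For the bridge, *assume* an SD of change of 30 to 40 s and an arm-related shift in calling form of 5 to 10 s:

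- 5/40 = 0.13 SD
- 5/30 = 0.17 SD
- 10/40 = 0.25 SD
- 10/30 = 0.33 SD

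Only the last exceeds the standard error of 0.28.

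With no true difference and a bias of b SD, the chance that a 95% interval excludes zero is Φ(b/SE − 1.96) + Φ(−b/SE − 1.96). For b = 0.2, b/SE = 0.707, giving Φ(−1.253) + Φ(−2.667) = 0.109. The synopsis (Section 5) gives 60 participants instead of 50, so both are shown.

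| Assumed bias (SD) | 50 participants | 60 participants |
|---|---|---|
| 0 | 5.0% | 5.0% |
| 0.1 | 6.4% | 6.7% |
| 0.2 | 10.9% | 12.1% |
| 0.3 | 18.6% | 21.3% |

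The estimate itself moves by the full bias, and a larger sample does not reduce that.

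**The case against.** The best case against runs as follows.

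- **Silence is not a statement.** The plan does not say that assessors know the arm, or that the same person informs, follows up and measures a participant. This stands. The point is a missing provision, not a described practice.
- **This is a pilot.** Its main aim is feasibility, and Section 17 says that it lacks the power for conclusions on efficacy. This stands and limits the weight of the point.
- **There are safeguards.** Alignment landmarks, the 120 s cap, the mock measurements and instrument readings narrow the room for judgement. For a participant who holds good form to the cap, leniency adds nothing. This stands in part, because training and mock measurements serve reliability and do not stop a consistent difference by arm.
- **The size is assumed.** This stands. No SD or bias for these measures is in the documents.

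Two stronger readings are tempting. A reader might infer that the physical tests are the trial's only objective support for the self-reported pain result, so that bias in them undermines the main finding. The documents never give the tests that role. A reader might also infer that the bias must favour hatha yoga. Section 7 credits postures with gains in strength and flexibility, and Section 9 describes restorative yoga as involving little exertion, so an assessor could hold that expectation. But the plan states no directional hypothesis and calls restorative yoga of interest in its own right.

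**Conclusion.** The point holds as an omission of moderate weight. Followed as written, the plan leaves the week 12 bridge times, and to a lesser extent grip strength, open to an avoidable bias that analysis cannot remove afterwards. The inclinometer reading is the least exposed. Assessor masking would change nothing for the primary outcome or for the outcomes named for the effect-size model.

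The documents support no estimate of the bias. The figures above show only that a bias of 0.2 to 0.3 SD, if it occurred, would be close to the standard error of 0.28 SD. They rest on about 25 per arm, a normal approximation, the assumed bias, and these measures being compared between arms with a 95% interval.

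**What to change.** In Section 9, under Assessments and Randomization and under Physical Measures, state that:

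1. where rostering among the staff already trained allows, week 12 physical measures are taken by a research assistant who did not randomise, inform or follow up that participant. The assistant who measured at baseline may qualify, since baseline precedes allocation;
2. participants are asked before testing not to reveal their class type;
3. scripted encouragement and a fixed written rule for loss of form are used at both visits;
4. the assessor records any unmasking, or a guess of the arm;
5. where masking is not possible at a site, this is reported as a limitation.

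The cost is a roster, a line in the visit script and an item on the form, with no added visit. Scheduling becomes slightly less flexible. The plan does not give the number of trained staff at each site, so item 1 is conditional and item 5 covers the case where it cannot be met. The change has to be made before week 12 measurements start, and the common script and form rule before baseline.
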